3.3.6.2 Monitoring and management of hypertension

In clinical studies with pazopanib, events of hypertension including hypertensive crisis have occurred. Hypertension (systolic blood pressure ≥ 150 or diastolic blood pressure ≥ 100 mm Hg) occurs early in the course of treatment (39% of cases occurred by Day 9 and 88% of cases occurred in the first 18 weeks).

Blood pressure should be well controlled prior to initiating pazopanib (see 2.1.2.5)

3.3.6.2.1 BP MONITORING:

- Check BP twice weekly for the first 2 months of therapy, then weekly for 2 months, and then once per month thereafter. On days that the patient is not scheduled for clinic visits, BP can be taken at home, local Pharmacy or local Physician's office.
- BP should be taken preferably in the morning and after resting for at least 5 minutes.
- If BP is ≥140/90, then it should be repeated twice (30 and 60 minutes after the first reading). The lowest of these 3 readings will be the one considered for grading and management purposes.
- If BP measured outside the clinic visits is ≥140/90, the result should be immediately reported to the Research Nurse and/or treating physician to take appropriate action as outlined below.

BP MANAGEMENT BASED ON GRADE (CTCAE 4.02):

Hypertension- Adverse Event Grade

Grade 1 (systolic 120-139, diastolic 80-89)

Management

- no need to modify or add anti BP meds; if the patient is already taking BP meds, reinforce need for compliance.
- continue pazopanib and topotecan at same doses.
- add or increase dose of BP meds (at the discretion of

Grade 2 (systolic BP 140-159 or

Version Date: 07/17/2025

diastolic 90-99)*

Page 24 of 96

the treating physician);

- continue topotecan;
- HOLD pazopanib at the discretion of the treating physician until AE recovers to grade 0-1, then restart same dose.

Grade 3 (systolic \geq 160 or diastolic \geq 100)

- add or increase dose of BP meds (at the discretion of the treating physician);
- continue topotecan;
- HOLD pazopanib until AE recovers to grade 0-1, then restart pazopanib reducing 1 dose level.
- DISCONTINUE pazopanib;
- patient finishes trial participation.

Grade 4 (malignant hypertension; transient or permanent neurologic deficit, hypertensive crisis)

*Note: for elevated BP to be considered grade 2 or 3 the patient should be previously normotensive or should be taking BP medication/s regularly.

3.3.6.2.2 IF THE PATIENT IS NOT COMPLIANT:

- REINFORCE need for strict compliance with current BP medication/s,
- HOLD pazopanib AND CONTINUE BP monitoring at least once a day until BP returns to grade 0-1,
- Then resume pazopanib at same dose.

THIS ELEVATED BP WILL NOT BE CONSIDERED AN AE UNLESS THERE IS A SECOND OCCURRENCE WHILE TAKING BP MEDICATIONS REGULARLY.

3.3.6.3 Management of QT Prolongation and Torsade de Pointes:

In clinical studies with pazopanib, events of QT prolongation or Torsade de Pointes have occurred. Pazopanib should be used with caution in patients with a history of QT interval prolongation, patients taking antiarrythmics or other medications that may potentially prolong QT interval, or those with relevant pre-existing cardiac disease. When using pazopanib, baseline and periodic monitoring of electrocardiograms and maintenance of electrolytes (calcium, magnesium, potassium) within normal range is recommended.

3.3.6.4 Management of Arterial Thrombotic Events:

In clinical studies with pazopanib, myocardial infarctions, angina, ischemic stroke and transient ischemic attack were observed. Fatal events have been observed. Pazopanib should be used with caution in patients who are at increased risk of thrombotic events or who have had a history of thrombotic events. Pazopanib has not been studied in patients who have had an event within the previous 6 months. A treatment decision should be made based upon the assessment of individual patient's benefit/risk.

3.3.6.5 Management of Hemorrhagic Events:

In clinical studies with pazopanib hemorrhagic events have been reported. Fatal hemorrhagic events have occurred. Pazopanib has not been studied in patients who had a history of hemoptysis, cerebral, or clinically significant gastrointestinal hemorrhage in the past 6 months. Pazopanib should be used with caution in patients with significant risk of hemorrhage.

Version Date: 07/17/2025 Page 25 of 96

3.3.6.6 Management of Gastrointestinal Perforations and Fistula:

In clinical studies with pazopanib, events of gastrointestinal (GI) perforation or fistula have occurred. Fatal perforation events have occurred. Pazopanib should be used with caution in patients at risk for GI perforation or fistula.

3.3.6.7 Wound Healing issues:

No formal studies on the effect of pazopanib on wound healing have been conducted. Since Vascular Endothelial Growth Factor (VEGF) inhibitors may impair wound healing, treatment with pazopanib should be stopped at least 7 days prior to scheduled surgery. The decision to resume pazopanib after surgery should be based on clinical judgment of adequate wound healing. Pazopanib should be discontinued in patients with wound dehiscence.

3.3.6.8 Hypothyroidism:

In clinical studies with pazopanib, events of hypothyroidism have occurred. Proactive monitoring of thyroid function tests is recommended.

3.3.6.9 Proteinuria:

In clinical studies with pazopanib, proteinuria has been reported. Baseline and periodic urinalyses during treatment are recommended and patients should be monitored for worsening of proteinuria. Pazopanib should be discontinued if the patient develops nephrotic syndrome.

3.3.6.10 Pregnancy:

Pre-clinical studies in animals have shown reproductive toxicity. If the patient becomes pregnant while receiving pazopanib or topotecan, the potential hazard to the fetus should be explained to the patient. Women of childbearing potential should be advised to avoid becoming pregnant while receiving treatment with pazopanib or topotecan. Pazopanib or topotecan should not be used during pregnancy or lactation.

3.3.6.11 Topotecan-induced neutropenic colitis:

Topotecan-induced neutropenia can cause neutropenic colitis. Fatalities due to neutropenic colitis have been reported in clinical trials with topotecan. In patients presenting with fever, neutropenia, and a compatible pattern of abdominal pain, the possibility of neutropenic colitis should be considered.

3.3.6.12 Interstitial lung disease:

Topotecan has been associated with reports of interstitial lung disease (ILD), some of which have been fatal. Underlying risk factors include history of ILD, pulmonary fibrosis, lung cancer, thoracic exposure to radiation and use of pneumotoxic drugs and/or colony stimulating factors. Patients should be monitored for pulmonary symptoms indicative of ILD (e.g. cough, fever, dyspnea and/or hypoxia), and topotecan should be discontinued if a new diagnosis of ILD is confirmed.

3.3.6.13 Diarrhea

Diarrhea, including severe diarrhea requiring hospitalization, has been reported during treatment with oral topotecan. The incidence of diarrhea has been reported to be greater in patients receiving oral topotecan compared to those receiving topotecan i.v. Additionally, in patients with relapsing small cell lung cancer, greater than 65 years of age, there is substantially higher risk of

Version Date: 07/17/2025 Page 26 of 96

severe diarrhea and subsequent hospitalization than in patients less than 65 years of age. Communication with patients prior to drug administration regarding diarrhea and proactive management of all signs of diarrhea is important. Physicians are advised to follow guidelines that describe the aggressive management of this event. This includes use of anti-diarrheal agents, administration of fluids and electrolytes and interruption or discontinuation of therapy with oral topotecan.

Diarrhea related to oral topotecan can occur at the same time as drug-related neutropenia and its sequelae.

3.3.6.14 At the Start of the Next Treatment Cycle:

A new course of treatment may begin when the ANC is at least 1500/mm³ and the platelet count is at least 75,000/mm³ and any other treatment-related toxicities are less than or equal to grade 1. If after a one-week delay, all treatment related toxicities are less than or equal to grade 1, then proceed with treatment at the dose level dictated by the modifications outlined above. If treatment related toxicities have not resolved to less than or equal to grade 1 after a one-week delay, then treatment will be held again, and the patient will be evaluated weekly. If treatment will be held for 2 weeks for treatment related toxicities, then reduce the pazopanib dose by one dose level beyond that indicated by whether or not the patient had DLT in the prior cycle. If retreatment must be held for more than 2 weeks the investigator should be notified. If a patient develops another DLT at the reduced dose or if they experience a life-threatening toxicity at any time, they will be removed from study.

3.4 ON STUDY EVALUATION

3.4.1 General Requirements

- 3.4.1.1 CBC with differential and platelets and serum chemistries and LFTs (ALT, AST and bilirubin) will be performed every two weeks X 2, (+/- 3 days) then every 4 weeks (+/- 3 days) prior to each cycle during treatment. UPC (+/- 3 days) will be done monthly prior to each cycle.
- 3.4.1.2 A brain MRI/CT for group B will be done monthly until 3 months then every other month thereafter, for group A scan will be obtained every other month prior to initiation of odd numbered 28 days treatment cycles (+/- 3 days).
- 3.4.1.3 All relevant information regarding drug doses, concomitant medications, and doses, measurable lesions with measurements, tumor response, laboratory examinations, and treatment-related toxicities shall be documented in the patient's medical record and flow sheets.
- 3.4.2 A complete Neurologic exam (to include documentation of the patients Karnofsky Performance Status) will be performed prior to every evaluation where an MRI is scheduled. The MDASI-BT (Appendix 15.5) will be completed at baseline and at the time of each evaluation that includes an imaging study.
- 3.4.3 The patient will complete the MDASI-BT (see Appendix 15.5) at the time of clinical evaluation with MRI as long as the clinical therapy is being administered, unless clinical deterioration makes self-report not possible before that time. The time when patients are unable to complete the self-report questionnaires will be used as part of the study analysis. The MDASI-BT will be completed only by the patient, unless changes in vision

Version Date: 07/17/2025 Page 27 of 96

or weakness make this difficult. If this occurs, then the caregiver or research assistant may read the questions to the patient or assist with marking the severity number or score as described by the patient. A patient caregiver may complete the questionnaires as a patient-preference proxy if the patient's deficits preclude self-report.

- 3.4.3.1 A measurement of BP should be taken twice weekly for the first 2 months of therapy, then weekly for 2 months, and then once per month thereafter as detailed in 3.3.5.2. BP can be assessed by any method (i.e., at home or by another physician) as long as the treating physician is informed of the measurement, verifies any measurement that is not normal and takes appropriate action.
- 3.4.3.2 Thyroid function test (T4 and TSH) (+/- 3 days) are to be monitored every 8 weeks (+/- 3 days)
- 3.4.3.3 EKG before treatment and week 4 and then every 8 weeks until end of treatment (+/- 3 days)

3.4.4 Follow-up

Patients will be evaluated for adverse events at the end of each cycle. In addition, all serious adverse events will be reported to the NCI BTTC as in section 8.6.

All patients will be followed for overall survival, when possible.

Patients who discontinue treatment due to progression will be followed for survival every 3 months.

Patients who come off therapy for reasons other than progression should be followed until progression or institution of new anti-tumor therapy. They should then be followed for survival.

3.5 **QUESTIONNAIRES**

The MDASI-BT will be utilized for this portion of the study. Full instruments are provided in the Appendix 15.5 In addition, information regarding demographics and treatment history will be collected as part of the larger study and used in this analysis.

The MDASI-BT consists of 23 symptoms rated on an 11-point scale (0 to 10) to indicate the presence and severity of the symptom, with 0 being "not present" and 10 being "as bad as you can imagine." Each symptom is rated at its worst in the last 24 hours. Symptoms included on the instrument include those commonly associated with cancer therapies, those associated with increased intracranial pressure, and those related to focal deficits. The questionnaire also includes ratings of how much symptoms interfered with different aspects of a patient's life in the last 24 hours. These interference items include: general activity, mood, work (includes both work outside the home and housework), relations with other people, walking, and enjoyment of life. The interference items are also measured on 0 - 10 scales. The average time to complete these instruments is 5 minutes. The MDASI-BT has been translated into 18 languages [17, 20]

3.6 STUDY CALENDAR

	Screening	Week	Week	Every 4	Every 8	End of	F/U ^m
		One	Two	wks	wks	tx	
Informed Consent	X						

Version Date: 07/17/2025 Page 28 of 96

	Screening	Week	Week	Every 4	Every 8	End of	F/U ^m
		One	Two	wks	wks	tx	
History/Physical Exam	X			X		X	
NeuroExam ^k	X				X		
Concomitant				X			
Meds/Adverse Events							
Vitals signs	X	Xa	Xa	X		X	
Performance Status	X			X		X	
Treatment Toxicity				X		X	
CBC ^g	X		X	X		X	
Chemistries, LFTs ^b	X		Xb	Xb		X	
Pregnancy test j	X					X	
UPC ratio	X			X			
UA	X						
Thyroid function test	X				Xc		
Coagulation test	X						
EKG ^d	X				Xd		
MRI or CT brain	X			Xe	Xf		
MDASI-BT ¹	X			X	X		
Tumor tissue	Xi						
Hepatitis Questionnaire	X						
Hepatitis B and C	Xn						

^a Monitoring of BP only: A measurement of BP should be taken twice weekly for the first 2 months of therapy, then weekly for 2 months, and then once per month thereafter. BP can be assessed by any method (i.e., at home or by another physician) as long as the treating physician is informed of the measurement, verifies any measurement that is not normal and takes appropriate action.

^b Monitoring of LFTs: LFTs (AST, ALT, Bili) every 2 weeks X 2, (+/- 3 days) then every 4 weeks prior to each cycle during treatment. (+/- 3 days)

^c Thyroid function test (T4 and TSH) are monitored every 8 weeks (+/- 3 days)

^dEKG: Week 4 and then every 8 weeks until end of treatment (+/-3 days)

^e MRI: Group B only: Every 4 weeks until 3 months, then every 8 weeks thereafter (+/- 3 days)

f MRI: Group A only: Scan will be obtained every other month prior to initiation of odd numbered 28 day treatment cycles (+/- 3 days)

^gCBC: Performed every 2 weeks X 2 (+/- 3 days) then every 4 weeks (+/3 days) prior to each cycle. For patients experiencing significant drop in WBCs or platelets felt related to Topotecan, CBCs should be obtained more frequently (weekly or more frequently) to assess timing for retreatment or need for G-CSF or transfusion support.

ⁱ Tumor tissue blocks or 15 unstained paraffin slides to be obtained from institutions where surgery performed and provided to collaborating neuro-pathologist for confirmatory tumor diagnosis. Patient may be enrolled prior to acquisition of tumor tissue block.

^J Only for women of childbearing potential; must be tested within 14 days prior to starting study drugs

Version Date: 07/17/2025 Page 29 of 96

- ¹ MDASI-BT should be completed by patient at the time of clinical evaluation with MRI.
- ^m Patient will be followed for overall survival when possible
- ⁿ If positive (+) response to Hepatitis questionnaire Hepatitis B and C screening test should be done.

3.7 CRITERIA FOR REMOVAL FROM PROTOCOL THERAPY AND OFF STUDY CRITERIA

- 3.7.1 Criteria for Removal from Protocol Therapy
 - 3.7.1.1 After administration of 12 28-day cycles of treatment, unless further treatment is felt to be in the best interest of the patient by the treating physician.
 - 3.7.1.2 Progression of disease (as defined in Section **6.4.1**).

Patients must be followed by the same type of brain scan, as was used for baseline tumor measurements, and will be removed from study if progression is documented after any cycle of treatment. Patients with stable disease, partial or complete response will continue on therapy.

- 3.7.1.3 Unacceptable toxicity (see Section 3.3).
- 3.7.1.4 The patient may withdraw from the study at any time for any reason.
- 3.7.1.5 Medical or psychiatric illness which in the investigator's judgment renders the patient incapable of further therapy.
- 3.7.1.6 Treatment delay due to toxicity greater than 21 days measured from the start of the preceding cycle.
- 3.7.1.7 All reasons for discontinuation of treatment must be documented in the flow sheets

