3.2 DRUG ADMINISTRATION

Patients will be treated with the combination of topotecan and pazopanib at the following doses:

3.2.1.1 Pazopanib: Starting dose is 600 mg (3x200mg) per day to be taken orally, daily, continuous, without food at least one hour before or two hours after a meal.

Pazopanib should be taken whole with water and must not be broken or crushed.

If a dose of pazopanib is missed, it should not be taken if it is less than 12 hours until the next dose.

3.2.1.2 Topotecan: Starting dose of topotecan is 0.25 mg orally, daily, continuous.

3.3 **DOSE MODIFICATIONS:**

3.3.1 For treatment or dose modification related questions, please contact the Academic PI or the BTTC Coordinating Center's Research Nurse [name]; [contact];

Version Date: 07/17/2025 Page 21 of 96

[contact], [contact]. Topotecan length of treatment is until progression, up to one year. Drug may be held up to 3 weeks waiting from toxicities to resolve. Drug dose will not be reduced.

3.3.2 Pazopanib length of treatment is until progression, up to one year. Dose of Pazopanib may be held up to 3 weeks waiting from toxicities to resolve and reduced to 400 mg or to 200 mg daily based on side effects. Patient may be maintained on the lower dose of pazopanib during protocol if deemed to be deriving benefit from the drug.

If a patient is felt to be deriving benefit for the agent(s) and is stable at the one year time point, based on discussion with the PI and sponsor it may be possible to continue treatment at that point.

3.3.3 Patients with stable or responding disease may be retreated at the same dose (both Topotecan and Pazopanib) or at a reduced dose level (pazopanib only), depending upon the adverse events observed in the current cycle and any adverse events present on the first day of the next cycle. If multiple toxicities are seen, the dose administered in a subsequent cycle should be based on the most severe toxicity experienced in the current cycle.

Dose modifications or delays should be made based upon whether toxicities occur within a 4-week treatment cycle or at the expected start of the next treatment cycle.

3.3.4 Within Treatment Cycles:

3.3.4.1 Topotecan:

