For patients who experience Grade 3 or 4 diarrhea, or other non-hematologic toxicities, the topotecan dose can be held up to 3 weeks waiting for toxicity to resolve to < Grade 2. Drug may be resumed at that time at same dose. If toxicity does not resolve in 3 weeks, patient will be taken off study. Patients with Grade 2 diarrhea may need to follow the same dose modification guidelines.

Topotecan should not be re-administered unless the neutrophil count is more than or equal to 1.5 x 10^9 /L, the platelet count is more than or equal to 75 x 10^9 /L, and the hemoglobin level is more than or equal to 9 g/dL (after transfusion if necessary).

Standard oncology practice for the management of neutropenia is either to administer topotecan with other medications (e.g. G-CSF) or to dose reduce to maintain neutrophil counts. Please refer to section 4.1 for protocol guideline regarding G-CSF administration.

3.3.4.2 Pazopanib:

For Pazopanib, two dose reductions are permitted, from 600 to 400 or 200 mg daily or from 400 to 200 mg daily. Further dose reduction is not allowed. Patients may be maintained on the lower dose of pazopanib during protocol if deemed to be deriving benefit from the drug. Doses that are reduced for pazopanib related toxicity will not be re-escalated, even if there is minimal or no toxicity with the reduced dose. Patients whose dose has been reduced for adverse events that are subsequently not felt to be related to pazopanib may have the dose re-escalated after completion of one cycle with toxicities less than or equal to grade 1.

3.3.5 Hematologic Toxicity:

Dose Modifications Based on ANC and Platelet Counts (topotecan):

Version Date: 07/17/2025 Page 22 of 96

ANC (/mL)	P	latelets (/mL)	% of Planned topotecar		
> 1500	and	> 75,000	100%		
< 750	or	< 50,000	hold*		

^{*}Topotecan should be held. Upon recovery to ANC $\geq 1,500/\text{mL}$ and platelets to >75,000/mL, the same dose level will be administered.

3.3.6 Non-hematologic Toxicity:

Dose Modifications Based on **topotecan- or pazopanib**-Related Non-Hematologic Toxicities:

NCI Grade	% of Planned Dose
0-2+	100%+
3*	hold**
4	hold***

+For symptomatic Grade 2 toxicity, the suspect drug dose may be held at the discretion of the investigator until recovery to CTC Grade 0-1, then resume at same dose for topotecan or one dose lower for pazopanib.

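### Section 3.7.1.6 counts its 21-day toxicity-delay limit from the start of a 28-day cycle, so every toxicity-delayed cycle start already breaches it

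*Combined protocol and SAP*

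**What the plan says.** **Removal rule.** Section 3.7.1.6 lists, among the reasons to stop protocol therapy, "Treatment delay due to toxicity greater than 21 days measured from the start of the preceding cycle".

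**Cycle length.** Section 3.7.1.1 ends treatment "After administration of 12 28-day cycles of treatment". Section 3.3.3 uses the same length and separates two situations: whether "toxicities occur within a 4-week treatment cycle or at the expected start of the next treatment cycle".

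**Permitted holds.**
- 3.3.1, topotecan: "Drug may be held up to 3 weeks waiting from toxicities to resolve. Drug dose will not be reduced".
- 3.3.2, pazopanib: "Dose of Pazopanib may be held up to 3 weeks waiting from toxicities to resolve".
- 3.3.4.1, topotecan with non-hematologic toxicity: "If toxicity does not resolve in 3 weeks, patient will be taken off study".
- 4.1.1.1, low counts: removal only after three weeks of hold without recovery.
- 3.3.6.14, start of the next cycle: treat after a one-week delay if toxicities have settled, otherwise hold again. A two-week hold lowers pazopanib by a further dose level. Beyond two weeks, the investigator is to be told.

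**Link to the endpoint.** Section 9 counts patients who drop out for toxicity as treatment failures in the two-stage designs.

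**Topotecan counts (secondary).** The 3.3.5 table gives full dose above ANC 1500 and platelets 75,000, and hold below ANC 750 or platelets 50,000. Section 4.1.1.1 holds below 1500 or 75,000. Section 3.3.4.1 sends the reader there, but only for growth factor: "Please refer to section 4.1 for protocol guideline regarding G-CSF administration".

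**The concern.** A removal criterion has to be applicable as printed, and this one is not. The clock in 3.7.1.6 starts a full cycle too early for a delay at a cycle boundary, so it orders removal in situations where section 3.3 tells the site to wait and then treat. Two sites that each follow a printed rule could handle the same patient differently.

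The primary endpoint is exposed because a dropout for toxicity is scored as a failure. A patient removed early under 3.7.1.6 who would otherwise have been progression-free at the landmark (6 months in Group A, 3 months in Group B) could lose a success. Stage 1 continues on 2 of 9 patients in Group A and 1 of 14 in Group B, so single scores carry weight.

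The count table raises a smaller question: someone working from 3.3.5 alone finds no instruction in the middle range.

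**Working it through.** The plan states no figure for this rule, so there is none to reproduce. The check is a day count, with all days measured as elapsed time from the start of the preceding cycle.

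**Inputs.** Cycle length 28 days (3.7.1.1; 4 weeks in 3.3.3). Removal limit 21 days from the start of the preceding cycle (3.7.1.6). Permitted hold 3 weeks = 21 days (3.3.1, 3.3.2, 3.3.4.1, 4.1.1.1).

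**Step 1: delay at a cycle boundary.** Elapsed days = 28 + d, where d is the delay past the due date.

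| Delay d | Elapsed days | Past the 21-day limit by | What section 3.3 allows |
|---|---|---|---|
| 1 | 29 | 8 | start once counts and toxicities have recovered |
| 7 | 35 | 14 | treat if toxicities are grade 1 or less, otherwise hold again |
| 14 | 42 | 21 | continue, pazopanib one further level down |
| 21 | 49 | 28 | last day of a 3-week hold, investigator notified |

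Every row exceeds 21. An on-time start, at 28 days, also lies beyond 21, but involves no toxicity delay and so is not caught.

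**Step 2: hold within a cycle.** If dosing stops s days into the cycle, the printed clock leaves 21 − s days, whereas 3.3.1 and 3.3.2 allow 21.

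| Hold begins at s | Days left under 3.7.1.6 | Days allowed under 3.3 |
|---|---|---|
| 7 | 14 | 21 |
| 14 | 7 | 21 |
| 20 | 1 | 21 |

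**Step 3: with the clock re-anchored.** Counting from the due date, removal at a boundary comes after 28 + 21 = 49 elapsed days. Counting from the first held dose, it comes after s + 21. Both match the 3-week holds.

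**Step 4: are the design's error rates affected as stated?** The exact probability of declaring promise is the sum over stage-1 counts x ≥ r1 of P(X1 = x) × P(X2 ≥ r − x), with X1 ~ Bin(n1, p) and X2 ~ Bin(n − n1, p).
- Group A (n1 = 9, r1 = 2, n = 34, r = 9): 0.0474 at p = 0.15 and 0.8107 at p = 0.35.
- Group B (n1 = 14, r1 = 1, n = 32, r = 2): 0.0287 at p = 0.01 and 0.8010 at p = 0.12.

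The stated 5% and 80% are met in both groups.

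**Step 5: counts, side by side (illustrative values).**

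| ANC | Platelets | 3.3.5 table | 4.1.1.1 |
|---|---|---|---|
| 700 | 100,000 | hold | hold |
| 1,000 | 100,000 | no instruction | hold |
| 1,600 | 60,000 | no instruction | hold |
| 1,600 | 80,000 | full dose | no hold |

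The table is silent in the middle range. It does not order dosing there.

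**The case against.** The strongest defence is that 3.7.1.6 is a plain drafting slip. The 21 days agree with the three weeks given everywhere else; only the starting point is off. Read literally, the rule would remove a patient whose next cycle began one day late, which no site is likely to do against the week-by-week rules in 3.3.6.14. Section 3.3.1 sends dose questions to the Academic PI, and 7.3.1 has the team discuss each patient every other week. Notification beyond two weeks and removal beyond three are successive steps and do not conflict. Patients who stop without progression are still followed for it (3.4.4, 3.7.2).

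Most of this stands. It makes literal use improbable and limits divergence that goes unnoticed. It does not correct the text: a site should not have to infer the starting point of a removal criterion, and a query arises only if someone sees a question. Continued follow-up keeps progression observable but does not undo the section 9 rule that scores a toxicity dropout as a failure.

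On the counts, a reader might infer that 3.3.5 directly contradicts 4.1.1.1 and keeps patients on full dose at mid-range values. The documents do not support that. The full-dose row requires both counts above the upper levels, 4.1.1.1 supplies the missing instruction, and 3.3.4.1, just above the table, already bars giving topotecan again below 1.5 and 75 × 10^9/L. The last rule can be read as applying to restarts only. The table also comes from PDF extraction, so a lost row, perhaps leaving the hold to the investigator's discretion, cannot be excluded.

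Nor is an effect on the endpoint shown. Take a count that is low at the two-week blood draw and never recovers. A three-week clock started then ends at 14 + 21 = 35 days; one started at the next boundary ends at 28 + 21 = 49. Both precede the 3- and 6-month landmarks, so the score is the same.

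**Conclusion.** The starting point of the clock in 3.7.1.6 is wrong as written and should be corrected. Every cycle start delayed by toxicity exceeds the limit, and the longest delay the 3-week rules permit lies 28 days beyond it (49 − 21). This rests only on the printed text and the 28-day cycle. That the authors meant 21 days from the due date or the first held dose is an inference, though a natural one.

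The link to the primary endpoint needs two further conditions: that a removal under 3.7.1.6 is treated as a toxicity dropout under section 9, and that it falls before the landmark in a patient who would otherwise have been a success. How many patients meet both cannot be derived from the documents. A reader might infer a loss of power; that would need a rate of wrongful removal, which the plan does not give. No stated alpha, power or sample size is in error.

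The gap in the 3.3.5 table is a secondary clarification, at lower confidence because the table may be incomplete as extracted. No claim about the endpoint attaches to it.

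**What to change.** **3.7.1.6.** Replace the starting point and keep the limit. Suggested text: *Treatment has been delayed by toxicity for more than 21 days, counted from the scheduled start of the delayed cycle or, when dosing was interrupted within a cycle, from the first held dose.* This follows the distinction that 3.3.3 already makes.

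**3.3.5 (secondary).** Add a row for ANC 750 to 1500 and platelets 50,000 to 75,000, or a pointer to the hold rule in 4.1.1.1. The clinical team should confirm the threshold first.

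**Cost.** One clarification amendment with IRB approval, and a memo to sites. No extra patients or scheduled visits. If the mid-range instruction is to hold, sites that had worked from the table alone may see somewhat more topotecan holds and the blood counts that go with them.
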